Appendix D. Criteria for Potentially Clinically Important Vital Sign Values

Vital Signs Variables	Criterion	Definition of Potentially Clinically Important
Systolic Blood	Low	Value ≤ 90 mmHg and decrease ≥ 20 mmHg from Baseline
Pressure (mmHg)	High	Value ≥ 160 mmHg and increase ≥ 20 mmHg from Baseline
Diastolic Blood	Low	Value ≤ 50 mmHg and decrease ≥ 10 mmHg from Baseline
Pressure (mmHg)	High	Value ≥ 100 mmHg and increase ≥ 10 mmHg from Baseline

Appendix E. Non-Responder Imputation Incorporating Multiple Imputation to Handle Missing Data Due to COVID-19 Pandemic for Dichotomized Outcome Variables

1.0 Overview

[figure not shown]
1.1 Background and Justification for Missing at Random (MAR) Assumption

The COVID-19 pandemic is interfering with the conduct of many ongoing trials, with potential impacts on treatment duration and the collection, analysis and the interpretation of clinical trial data. Some protocol-specified visits in the clinical trials may be impacted due to COVID-19 infection or logistical restrictions during the pandemic. For example, some scheduled visits may be missed due to self-quarantine or local government restrictions on travel; some visits may also be delayed or canceled due to healthcare resource constraints during the pandemic. Impacted visits due to COVID-19 will be recorded in the database. The probability of having missed visits and missing data due to COVID-19 infection or logistical restrictions related to the COVID-19 pandemic can be reasonably assumed to be unrelated to the unobserved values. Therefore, for the purpose of statistical analysis, it is reasonable to assume that these missing data are missing at random (MAR) and the statistical models that require MAR assumption are appropriate. In some cases, sensitivity analyses may be performed to assess the impact of missing data and the robustness of the conclusion.

1.2 FDA Guidance

FDA provided two guidance documents^{1,2} in March 2020 and June 2020 on the efficacy collection and possible changes in the statistical analysis plan:

"With respect to efficacy assessments, FDA recommends consultation with the
appropriate review division regarding protocol modifications for the collection
of efficacy endpoints, such as use of virtual assessments, delays in assessments,
and alternative collection of research-specific specimens, if feasible. For
individual instances where efficacy endpoints are not collected, the reasons for
failing to obtain the efficacy assessment should be documented (e.g.,

- identifying the specific limitation imposed by COVID-19 leading to the inability to perform the protocol-specified assessment)."
- "If changes in the protocol will lead to amending data management and/or statistical analysis plans, the sponsor should consider doing so in consultation with the applicable FDA review division. Prior to locking the database, sponsors should address in the statistical analysis plan how protocol deviations related to COVID-19 will be handled for the prespecified analyses."

1.3 EMA Guidance

EMA provided guidance³ in March 2020:

- "At this point in time it is not possible to give general applicable advice on how
 the different aspects related to the pandemic should be handled, as implications
 on clinical trials are expected to be manifold. Impact on the data collection,
 analysis and interpretation of results for each trial will need a thorough case-bycase assessment."
- "As a general principle, there are strong scientific reasons to conduct trials as planned and implement changes only when there is a convincing scientific reason that it improves interpretability of results."

1.4 Missing Data Handling for Missing Due to COVID-19 for Dichotomized Variables

In this document, a missing data handling method is proposed to handle missing data due to COVID-19 infection or logistical restrictions related to the COVID-19 pandemic under the general MAR framework. In particular, we explain using multiple imputation (MI) to handle missing data due to COVID-19 in dichotomized variables in conjunction with non-responder imputation (NRI) for missing data due to other reasons.

2.0 Non-Responder Imputation incorporating multiple imputation to handle missing data due to COVID-19 (NRI-C)

2.1 Overall Description of the Method

[figure not shown]
For a dichotomized outcome variable with missing data, the NRI-C will categorize any subject who does not have evaluation during a pre-specified visit window as a non-responder for the visit, with two exceptions:

- If the subject is a responder both before and after the pre-specified visit window in the particular Study Period, the subject will be categorized as a responder for the visit.
- If the reason for missing (e.g., missed visits, incomplete visit, out-of-schedule visits, or discontinuations of study drug) is due to COVID-19, the information will be captured in the database and the subject's response status will be imputed using multiple imputation.

Of note, later visits of subjects receiving any antibiotics for HS-related infections or discontinued study drug due to lack of efficacy will be set as missing before imputation. As a result, these assessments will not contribute to the imputation and the subjects will be counted as non-responders for the analysis at later visits. When determining the HiSCR response status, a subject with missing Baseline value will be counted as a non-responder at any post-baseline visit unless a subject's abscess, inflammatory nodule, and draining fistula counts are all zero at a specific visit, then the subject will be a HiSCR responder at that visit. NRI-C will be implemented as follows.

2.2 Multiple Imputation (MI) and MAR Assumption

When a dichotomized variable is derived from continuous scales, for example, HiSCR (as at least a 50% reduction in the total abscess and inflammatory nodule (AN) count with no increase in abscess count and no increase in draining fistula count relative to Baseline), the multiple imputation will be applied to the original scales of abscess, inflammatory nodule and draining fistula counts, assuming multivariate normal distributions. Then the

dichotomized variable will be derived from the imputed values. For demonstration purposes, we use HiSCR as an example in this Appendix E, and provide sample code for the imputation of abscess count in Appendix E Section 3.0. The same imputation strategy will be applied to the inflammatory nodule count and the draining fistula count. HiSCR status will be determined accordingly.

The MI procedure assumes that the data are missing at random (MAR). That is, for an outcome variable Y, the probability that an observation is missing depends only on the observed values of other variables, not on the unobserved values of the outcome variable Y. Statistical inference from the MI procedure is valid under the MAR assumption.

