Multiple Imputation (MI) will be used as a sensitivity analysis for the primary endpoint (HiSCR at Week 16). PROC MI with the Markov Chain Monte Carlo (MCMC) statement will be first applied to generate 30 augmented datasets with monotonic missing pattern. The random seed for the MCMC will be the SAS numerical value of the first subject randomization date. PROC MI will then be used to impute 30 complete datasets using the regression method. The random seed for this imputation step will be the SAS numerical value of the last subject randomization date. Taking abscess count as an example, the variables to be included in the imputation model are: treatment group, prior exposure to anti-TNF category, Baseline worst Hurley Stage, Baseline abscess count, and abscess counts at each visit up to the end of the double blind Period A. The imputed post-baseline abscess counts will be rounded to the same precision as the observed data to determine the responder status. The same imputation strategy will be applied to the inflammatory nodule count and the draining fistula count. HiSCR status will be determined accordingly. Using the Cochran-Mantel-Haenszel (CMH) model adjusted by actual stratification factors, the imputed endpoints will be analyzed using each of the 30 datasets. SAS PROC MIANALYZE will be used to generate the final inferences of the risk difference between each risankizumab dose and placebo. Note that measurements will be considered as missing after receiving any antibiotics for HS-related infections or discontinued study drug due to lack of efficacy before MI. Regardless of MI imputed values, subjects receiving any antibiotics for HS-related infections or discontinued study drug due to lack of efficacy will be counted as non-responders at later visits.

Observed Case (OC) analysis will only be performed during the Primary Analysis for the summaries of categorical endpoints for visits after Week 16. The OC analysis will not impute values for missing evaluations, and thus a subject who does not have an evaluation on a scheduled visit will not be included for that visit. The OC analysis will not include values after receiving any prohibited antibiotics for HS-related infections or after discontinued study drug due to lack of efficacy.

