2.3 Imputation Algorithm

[figure not shown]
It is reasonable to assume the missing values of the longitudinal data for an outcome variable (e.g., abscess count at each post-baseline visit) follows a monotone missing pattern. In practice, the missing data of the outcome variable might have an arbitrary (non-monotone) missing data pattern. An extra step may be added accordingly, to augment data into a monotone missing pattern.

For the outcome variable (e.g., abscess count at each visit), K 'complete' datasets can be generated in two steps: augmentation step and imputation step. K, the number of repetitions, is determined below.

Augmentation Step

For datasets with non-monotone missing data pattern, the augmentation step will first impute enough values to augment the data into a monotonic missing pattern:

Markov Chain Monte Carlo (MCMC) will be applied to augment the data using PROC MI with the MCMC IMPUTE=monotone statement, assuming a multivariate normal distribution. The augmented data will be used in the subsequent imputation step to generate 'complete' datasets. Covariates included in the model are treatment group, prior exposure to anti-TNF category, Baseline worst Hurley Stage, Baseline abscess count, all

post-baseline visits of abscess count up to the end of the Study Period. Of note, categorical variables are included using the form of dummy variables.

Repeat the imputation process K=30 times using the procedure described above to form K=30 monotone missing datasets, where K is determined as described in "Repetition of Imputations (K)."

Imputation Step

For missing data with monotone missing patterns, the choice of multiple imputation using a parametric regression model that assumes multivariate normality is appropriate.

The imputation step is described below:

- The imputation model for the missing data is a regression model, which controls for treatment group, prior exposure to anti-TNF category, Baseline worst Hurley Stage, Baseline abscess count, all post-baseline visits of abscess count up to the end of the Study Period. The covariates included in the model and the order of these variables are consistent with the augmentation step.
- For each monotone missing dataset, using SAS PROC MI with MONOTONE REG model statement, the outcome variable at each post-baseline visit with missing values will be imputed sequentially with covariates constructed from their corresponding sets of preceding variables.

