2.4 Derivation of Response Status and Non-Responder Imputation

Same as the abscess count, we also impute to obtain complete datasets for the inflammatory nodule count and the draining fistula count. For each 'complete' dataset, the imputed post-baseline values will be rounded to the same precision as the observed data. HiSCR status will be determined accordingly.

The imputed response status for missing due to reasons other than COVID-19 will be overridden by non-responder imputation (Section 2.1) to ensure that multiple imputation is only applied to missing due to COVID-19:

- Using NRI-C approach, all missing due to reasons other than COVID-19 will be categorized as non-responders, including visits after a subject receives any antibiotics for HS-related infections or discontinued study drug due to lack of efficacy. When determining the HiSCR response status, a subject with missing Baseline value will be counted as a non-responder at any post-baseline visit unless a subject's abscess, inflammatory nodule, and draining fistula counts are all zero at a specific visit, then the subject will be a HiSCR responder at that visit.
- The only exception is that a subject will be categorized as a responder for the visit if the subject is a responder both before and after an SAP-specified visit window in the particular Study Period.

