3.0 Sample SAS Code

```
/*********
/*IMPUTATION ALGORITHM*/
/*********
/*NOTE: THIS APPROACH REQUIRES NO MISSING IN CATEGORICAL COVARIATES AND
REQUIRES AT LEAST ONE OBSERVATION IN BASELIBE OR ONE OF THE POST-
BASELINE VISIT*/
/*PRE-AUGMENTATION - CREATE DUMMY FOR CATEGORICAL VARIABLES*/
/***************
DATA COUNT 2; SET COUNT;
 /*THE MCMC STATMENT BELOW ASSUMES MULTI-VARIATE NORMAL*/
 /* USE ALL DATA IN THE IMPUTATION MODEL*/
 IF TRT01P="180mg" THEN TRT1=1; ELSE TRT1=0; /* CREATE DUMMY TREATMENT
VARIABLE FOR THE ANALYSIS STAGE*/
 IF TRT01P="360mg" THEN TRT2=1; ELSE TRT2=0; /* CREATE DUMMY TREATMENT
VARIABLE FOR THE ANALYSIS STAGE*/
 IF HURLEY=1 THEN HURLEY1 = 1 ELSE HURLEY1 = 0; /* CREATE DUMMY
VARIABLE FOR HURLEY STAGE 1*/
 IF HURLEY=2 THEN HURLEY2 = 1 ELSE HURLEY2 = 0; /* CREATE DUMMY
VARIABLE FOR HURLEY STAGE 2*/
/*AUGMENTATION STEP -- TO HAVE 30 MONOTONE MISSING DATASETS*/
PROC MI DATA= COUNT 2 OUT= COUNT MONO NIMPUTE=30 SEED= 21423 /*RANDOM
SEED PRE-DEFINED*/
 ROUND=. . . . . 1 1 1 1 1 1 1 /*VALUE ROUND TO INTEGER*/
 MIN=. . . . 0 0 0 0 0 0 0 0 /*MINIMUM VALUE OF COUNT IS 0*/
 MAX=. . . . . . . . . /*MAXIMUM VALUE*/
MCMC IMPUTE=MONOTONE ;
/*NOTE: CATEGORICAL VARIABLES SUCH AS TRT1 TRT2 HURLEY1 HURLEY2 ARE
DUMMY, CREATED ABOVE*/
/*NOTE: ALL OTHER NON-DUMMIED COVARIATES MUST BE CONTINUOUS*/
VAR TRT1 TRT2 TNFN HURLEY1 HURLEY2 BASE WK1 WK2 WK4 WK8 WK12 WK16;
/*CAUTION TO USE THE "BY" STATEMENT IN MCMC: */
```

```
/*MVN MODEL IS FITTED WITHIN EACH 'BY' GROUP, INSTEAD OF ACROSS ALL
GROUPS*/
RUN;
/*IMPUTATION STEP - DETERMINE IMPUTATION DISTRIBUTION AND RANDOMLY
IMPUTE MISSING VALUE TO GENERATE 'COMPLETE' DATASETS*/
/****************
PROC MI DATA= COUNT MONO OUT= COUNT FULL NIMPUTE=1 SEED= 21931 /*RANDOM
SEED PRE-DEFINED*/
 ROUND=. . . 1 1 1 1 1 1 1 /*VALUE ROUND TO INTEGER*/
 MIN=. . . 0 0 0 0 0 0 0 /*MINIMUM VALUE OF COUNT IS 0*/
 MAX=. . . . . . . . /*MAXIMUM VALUE*/
 MINMAXITER=1000;
 /*CLASS CATEGORICAL VARIABLES TRT1 AND REG2*/
 CLASS TRT01P TNFN HURLEY;
 VAR TRT01P TNFN HURLEY BASE WK1 WK2 WK4 WK8 WK12 WK16;
 MONOTONE REG (WK1 WK2 WK4 WK8 WK12 WK16); /* IMPUTED SEQUENTIALLY,
FROM WK 1 TO 16, WITH COVARIATES CONSTRUCTED FROM THE CORRESPONDING
PRECEDING VARIABLES*/
 BY IMPUTATION;
                                 /*FOR EACH OF THE 30 MONOTONE
MISSING DATASETS, IMPUTE A 'COMPLETE' DATASET*/
RUN;
/*We will get the imputed "complete" datasets for abscess, inflammatory
nodule, and draining fistula counts. For sample code below, we denote

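### Imputing small lesion counts from a normal model biases imputed HiSCR towards non-response and weakens the MI sensitivity analysis of the primary endpoint

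*SAP*

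**What the plan says.** HiSCR needs three things at once: the AN count at least halved, no more abscesses than at Baseline, and no more draining fistulas than at Baseline (SAP Section 3.1). Eligibility requires an AN count of at least 5 and at most 20 draining fistulas (protocol Section 5.1, items 7 and 9). It sets no minimum for abscesses or fistulas alone, so a Baseline of zero is allowed for either.

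Appendix E Section 2.2 states that "the multiple imputation will be applied to the original scales of abscess, inflammatory nodule and draining fistula counts, assuming multivariate normal distributions". Section 2.3 adds that, for monotone patterns, "the choice of multiple imputation using a parametric regression model that assumes multivariate normality is appropriate". Each lesion type has its own model. For abscesses the model holds treatment group, prior anti-TNF exposure, worst Hurley stage, and "Baseline abscess count, and abscess counts at each visit up to the end of the double blind Period A" (SAP Section 9.2.1). The other two lesion types follow the same strategy. On rounding, Section 9.2.1 says: "The imputed post-baseline abscess counts will be rounded to the same precision as the observed data to determine the responder status". The text gives no lower bound. The sample code (Appendix E Section 3.0) adds one, with the comment "MINIMUM VALUE OF COUNT IS 0" and the option "MINMAXITER=1000".

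This procedure serves two analyses:

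- **NRI-C (primary).** Only COVID-19-related gaps keep their imputed value: "The imputed response status for missing due to reasons other than COVID-19 will be overridden by non-responder imputation".
- **MI (sensitivity).** Missing values are imputed whatever the reason, except that subjects with HS-related antibiotics or lack-of-efficacy discontinuation stay non-responders at later visits.

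Section 9.3.3 lists one other sensitivity analysis, in the per-protocol population, and it handles missing data in the same way.

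**The concern.** A normal draw around a small mean spreads over fractional and negative values, whereas a real lesion count near zero sits mostly at exactly zero. After rounding, a subject with zero abscesses at Baseline becomes a non-responder on any draw of 0.5 or more, and likewise for fistulas. If negative draws are discarded and redrawn, as the code's minimum and iteration limit suggest, exact zeros become rarer still. Because all three HiSCR conditions must hold, an error in any one count can turn a responder into a non-responder.

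At stake is the purpose of the MI analysis. It should show what happens when missing data are treated as missing at random instead of as failures. If its imputed values are themselves tilted towards failure, part of any agreement with NRI-C is an artefact.

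**Working it through.** **1. The plan's own figure.** The SAP gives no figure for imputation bias. Its only relevant numbers are the design rates (26% placebo; 39.5-50% on 180 mg; 53% on 360 mg; 74 per arm; two-sided 0.025 per dose) and the power for at least one dose, 83.9 / 87.6 / 90.6%. Exact enumeration with a shared placebo arm gives 84.5 / 88.0 / 91.0% for a continuity-corrected test and 84.8 / 88.2 / 91.1% for Fisher's test. Both are within one point of the SAP. The uncorrected pooled test gives 88.5 / 91.4 / 93.7%. The design rates can therefore serve as the base.

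**2. One count.** Let the draw be normal with mean m and SD s. The chance that it ends as 0 is:

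- no redraw (values below 0 count as 0): Φ((0.5−m)/s)
- redraw if the rounded value is below 0: [Φ((0.5−m)/s) − Φ((−0.5−m)/s)] / [1 − Φ((−0.5−m)/s)]
- redraw if the raw value is below 0: [Φ((0.5−m)/s) − Φ(−m/s)] / [1 − Φ(−m/s)]

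| m, s | No redraw | Redraw, rounded | Redraw, raw | Poisson, same mean |
|---|---|---|---|---|
| 0, 2 | 0.60 | 0.33 | 0.20 | 1 |
| 0.5, 1 | 0.50 | 0.41 | 0.28 | 0.61 |
| 1, 1.5 | 0.37 | 0.25 | 0.16 | 0.37 |

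**3. Whole endpoint.** Three simulations, each with a different count model, imputed each lesion type by normal regression, rounded, and derived HiSCR. All count distributions and missing rates are assumptions.

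- *First* (negative-binomial Baselines, 12 scenarios, response calibrated to about 26 / 46.5 / 53%). Ratio of imputed to true HiSCR among missing subjects:

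| Missing | Redraw | No redraw |
|---|---|---|
| Week 16 only | 0.53-0.82 | 0.73-0.87 |
| Weeks 12 and 16 | 0.33-0.69 | 0.58-0.79 |
| From Week 4 on | 0.20-0.56 | 0.45-0.71 |

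- *Second* (Poisson-lognormal, redraw if raw value below 0). Middle scenario, Week 16 only: 8.8% imputed against 25.6% true on placebo (ratio 0.34) and 20.5% against 52.9% on 360 mg (0.39). Middle scenario, dropout: 5.4% against 27.0% and 13.2% against 50.7%. Mildest case, with almost no zero Baselines: 16.4% against 26.7% and 42.6% against 57.0%.
- *Third*: about 0.67-0.94 without redraw and 0.46-0.78 with redraw.

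Imputed response was below true response in every arm, missing pattern and bounding rule.

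**4. Effect on the treatment difference.** With missing share f and imputed response q in each arm, loss = f × [(0.53 − q360) − (0.26 − qPBO)]. Full non-responder imputation sets both q to 0, so its loss is f × 27 points.

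- *NRI-C, 5-10% COVID-missing.* First simulation (Week 16, or Weeks 12 and 16): 0.2-1.5 points with redraw, 0.1-0.6 without. Second simulation, dropout, f = 0.10: 0.10 × [(53 − 13.2) − (26 − 5.4)] = 0.10 × 19.2 = 1.9 points.
- *Power for 360 mg alone, 10% missing (pooled formula without correction).* From 87.8% to 84.4-87.0% with redraw or 86.4-87.5% without (first simulation), and to 83.2% (second). It is 80.9% if all 10% were non-responders.
- *MI, 20% missing.* Full non-responder imputation loses 0.20 × 27 = 5.4 points. In the first simulation MI loses 0.7-3.7 with redraw (13-69% of 5.4) or 0.4-1.6 without (7-30%). In the second it loses 0.20 × 19.2 = 3.8 points (70%).

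**5. Same task with predictive mean matching.** In the second simulation's middle dropout scenario at 10% missing, matching gave 21.9% and 43.8% against true 27.0% and 50.7% (ratios 0.81 and 0.86). The third gave about 0.84-1.07. Matching in the second simulation also treated the lesion types separately, so the normal shape is the main cause and separate modelling a smaller one. In the first simulation, modelling the types jointly raised the matching ratio from 0.84-0.96 to 0.90-0.98 (Week 16 only) and from 0.61-0.95 to 0.80-1.02 (from Week 4 on).

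**The case against.** **Size is not established.** This stands. The second simulation's 0.34-0.39 lies outside the first's 0.53-0.82 for the same missing pattern, so the ranges illustrate assumptions and are not bounds for this trial.

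**Redraw is only inferred.** This also stands. The governing text says to round and gives no minimum, and the documents do not describe how the software applies the bound. On the text reading, MI reproduces 7-30% of the non-responder shift and keeps most of its contrast. The direction survives, though: without redraw, imputed response was still too low throughout.

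**The mechanism is not universal for a single count.** True: at m = 1, s = 1.5, without redraw, the normal and Poisson chances of zero agree. The row with mean 0 and SD 2 is an extreme illustration. The bias appears in the composite endpoint, where all three conditions must hold.

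**20% missing may be too high.** Fair. Protocol Section 5.6 keeps subjects who stop drug on their scheduled visits. Subjects with HS-related antibiotics or lack-of-efficacy discontinuation are non-responders by definition of the estimand, so they do not belong in that 20%.

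**Power is not on the SAP's basis.** Correct. The 87.8% is for one dose without continuity correction and serves only to compare cases.

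**The sample code.** A reader might infer that the primary analysis would lose its non-responder override, because the override is written to ALLF while the analysis restarts from ALL. The documents do not support that. The governing text is explicit that "all missing due to reasons other than COVID-19 will be categorized as non-responders, including visits after a subject receives any antibiotics for HS-related infections", ALL is the right dataset on the MI path, and the listing is a sample with a declared placeholder. PROC STDRATE reads FREQ TABLE2, which is never created, but that would stop the run visibly. These are editorial slips.

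**Conclusion.** The concern holds as a worthwhile, inexpensive improvement. Normal regression on small, skewed counts biases imputed HiSCR towards non-response, more so if negative values are redrawn. Confidence is high on direction and low on size: the ratios of roughly 0.45-0.94 without redraw and 0.2-0.8 with redraw rest entirely on assumed count distributions and monotone missing patterns.

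A reader might infer that the primary result is unreliable or could be falsely positive. Neither follows. In NRI-C only COVID-19-missing data are affected, response falls in each arm, the difference shrinks by at most about 2 of 27 points in the cases tried at 5-10% missing, and no threat to type I error was seen. What is lost is some of the independence of the MI check: it lands between a fair missing-at-random analysis and non-responder imputation, so agreement with NRI-C should be read with that in mind.

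**What to change.** In SAP Section 9.2.1 and Appendix E Sections 2.2-2.3, for both NRI-C and MI, replace the normal regression draws with predictive mean matching on the counts. Preferably let the three lesion types act as predictors of one another. The augmentation step for non-monotone patterns should likewise avoid normal draws with a minimum of 0. The rest of the procedure (30 imputations, CMH risk difference, Rubin's rules, the non-responder override) can stay.

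The cost is SAP wording and minor reprogramming before unblinding for the Primary Analysis, with care for sparse strata such as Hurley stage I. No new data or subjects are needed. Direct logistic imputation of HiSCR could be added as a further sensitivity analysis but is not required.

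Editorial: in the sample code, run the NRI-C path from ALLF, and have PROC STDRATE read a table that is created, with zero-responder cells set to 0.
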